#### **When the MTD has been exceeded:**

When the MTD has been exceeded, the next lower dose previously studied will be evaluated for the MTD criteria. If only 3 subjects have been treated at this dose level, 3 additional subjects will be entered into this dose level until 6 subjects total have been treated.

- Once 6 subjects have been enrolled and evaluated at this dose level, if there was  $\leq 1$  DLT, this dose level will be declared the MTD.
- If  $>1$  DLT occurred, then the MTD has been exceeded, and the next lower dose level will be similarly evaluated.
- Dose level -1 will only be tested if dose level 1 exceeds MTD.

### 5.2.2. Definitions of Dose-Limiting Toxicity (DLT)

For the purpose of determining the MTD (see Section 5.2.3), DLT is defined as any of the following that are determined to be related to study treatment during **Cycle 1**:

- Grade 4 neutropenia (absolute neutrophil count [ANC] <500/ $\mu$ L) for >7 days.
- Febrile neutropenia (ANC <1000/ $\mu$ L with fever >101°F [38.5°C]).
- Grade 3 thrombocytopenia with  $\geq$  Grade 2 bleeding.
- Grade 4 thrombocytopenia (platelets <25,000/ $\mu$ L) > 7 days (patients may receive platelet support/transfusion).
- $\geq$  Grade 2 neuropathy with uncontrolled pain
- $\geq$  Grade 3 non-hematologic drug-related toxicity (excluding alopecia) despite optimal supportive care lasting >72 hours or requiring a dose reduction in the first cycle.
- Patients who are unable to receive 75% of the required doses of both agents secondary to toxicity.

Adverse events will be graded using the National Cancer Institute (NCI) Common Toxicity Terminology Criteria for Adverse Events v4.0 (CTCAE v4.0).

Dose modifications are not permitted during Cycle 1 in any cohort unless the subject experiences a DLT. Subjects in dose level -1 (see Table 2) who develop a DLT during Cycle 1 will be discontinued from the study. Subjects in dose level 1 or higher who experience a DLT during Cycle 1 will have treatment held. The DLT will be counted toward the assessment of the MTD for the given cohort; however, the subject may continue on therapy if the toxicity resolves and dose modifications can be implemented according to the dose modification guidelines in Section 6.0.

Patients who withdraw from the study before receiving 75% of their scheduled Cycle 1 doses due a non-drug related AE (i.e., tumor progression) will be considered inevaluable and will be replaced.

Patients without clinical evidence of progressive disease at the end of the first cycle of study therapy will continue treatment. Patients will be reevaluated for response after completing 2 cycles (8 weeks) of treatment. Patients with objective response or stable disease according the International Myeloma Working Group Uniform Response Criteria (see Appendix C) will continue treatment, with reevaluations until disease progression occurs, unacceptable toxicity develops, or the subject chooses to discontinue study treatment.

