## 5. STUDY DESIGN

This is an open-label, non-randomized Phase I/II study of patients with relapsed or refractory multiple myeloma.

The Phase I study will determine the MTD of the combination of carfilzomib and panobinostat. The Phase I portion will follow a standard dose escalation design, beginning with dose level 1 (see Table 2). Patients will be assessed for dose-limiting toxicity (DLT) at each visit during Cycle 1 prior to receiving treatment. Dose modifications will not be permitted during Cycle 1 unless a patient experiences a DLT (see Section 5.2.2.). Treatment cycles will be administered at 28-day intervals. Panobinostat will be administered orally three times weekly during weeks 1 and 3 of each cycle (Days 1, 3, 5, 15, 17, 19). Carfilzomib will be administered intravenously on Days 1, 2, 8, 9, 15, and 16 of each cycle. During Cycle 1, the carfilzomib dose will be escalated after the Day 2 dose, if well tolerated.

A maximum of four dose levels were evaluated. No DLTs were seen during the Phase I portion.

In the Phase II portion of this study, patients with relapsed/refractory multiple myeloma will receive treatment with the dose level 4 panobinostat and carfilzomib combination. Patients will be reevaluated for response to treatment after each cycle (4 weeks). Patients with objective response or stable disease will continue treatment, with subsequent reevaluations every 4 weeks, until disease progression or unacceptable toxicity occurs.

[figure not shown]
A parallel Phase I study will occur to evaluate a minimum of 3 patients and a maximum of 6 patients following a standard dose escalation design at additional dose levels of the combination of carfilzomib and panobinostat (see Table 3).

If additional dose levels are found to be tolerable, then additional patients will be recruited into an expansion cohort which will be open at all sites - a maximum total of 36 patients (including the ones recruited into the parallel Phase I study) will be treated at this dose level. Sites will be notified about the expansion cohort and patients will enter in the dose level confirmed in their enrollment confirmation from SCRI Innovations.

Up to 80 eligible patients will be treated in the Phase I/II study. The treatment schema for the study is shown in Figure 2.

Figure 2

Treatment Schema

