**Table 3. Parallel Dose Escalation Study – Dose Levels 5 and 6**

28-Day Cycles	Cycle 1	Cycle 2 to Progression
Dose Level 5		
Carfilzomib	20 mg/m  IV D 1, 2 / 56 mg/m  IV D 8, 9, 15, 16	56 mg/m  IV D 1, 2, 8, 9, 15, 16
Panobinostat	30 mg D 1, 3, 5, 15, 17, 19	30 mg D 1, 3, 5, 15, 17, 19
Dose Level 6		
Carfilzomib	20 mg/m  IV D 1, 2 / 56 mg/m  IV D 8, 9, 15, 16	56 mg/m  IV D 1, 2, 8, 9, 15, 16
Panobinostat	20 mg D 1, 3, 5, 15, 17, 19	20 mg D 1, 3, 5, 15, 17, 19

A parallel Phase I study will occur to evaluate a minimum of 3 patients and a maximum of 6 patients following a standard dose escalation design at additional dose levels of the combination of carfilzomib and panobinostat.

Patients will enter in the dose level confirmed in their enrollment confirmation from SCRI Innovations.

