### 5.2.1. Dose Escalation Phase I

The study will follow a standard dose-escalation design (see Table 2). For each cohort, the decision whether to dose-escalate will be made once all subjects have been

enrolled into the cohort and have received one full cycle (28 days) of study drug treatment. The following dose-escalation rules will be used:

- Initially, 3 subjects will be entered into a dose level.
- If 2 or more of the initial subjects experience dose-limiting toxicity (DLT) (see Section 5.2.2), then the MTD (see Section 5.2.3) has been exceeded.
- If none of the 3 subjects initially enrolled into this dose level cohort experiences DLT, then subsequent subjects will be enrolled in the next higher dose level.
- If 1 of the initial subjects experiences DLT, then 3 additional subjects (to a total of 6 subjects) will be enrolled in the dose level.
- If it is found that 1 of the 6 subjects in the dose level encounters DLT, then subsequent subjects will be enrolled into the next higher dose level cohort.
- If it is found that 2 or more of the 6 subjects in a dose level encounter DLT, then the MTD has been exceeded. If  $\geq 2$  of 6 patients have DLT on the first dose level tested (Dose Level 1, Table 2), dose level -1 will be evaluated. If dose level -1 is too toxic ( $\geq 2$  of 6 patients with DLT), the study will continue only after discussion by the study chair and the sponsors.

No intra-patient dose escalation is permitted.

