### **5.3. Phase II**

If a dose level in the parallel Phase I study is found to be tolerable, then additional patients will be recruited into an expansion cohort of 30 patients for Phase II for a total of 60 Phase II patients (including 30 patients for dose level 4).. A maximum of up to 80 total patients may be enrolled in this study (including patients from the dose escalation Phase I studies).

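### The febrile-neutropenia DLT gives 101°F and 38.5°C as one cut-off, but they differ by 0.17°C, so Cycle 1 fevers of 38.4 or 38.5°C count in one unit and not in the other

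*Combined protocol and SAP*

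**What the plan says.** Section 5.2.2 opens its list with "DLT is defined as any of the following that are determined to be related to study treatment during Cycle 1". One item is febrile neutropenia: an ANC below 1000/µL with "fever >101°F [38.5°C" (the bracket closes straight after the Celsius figure). The Fahrenheit value carries the inequality sign, and the Celsius value stands in brackets as its equivalent.

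Table 5 in Section 6.1 covers the same event for dose adjustment. It uses Celsius only, with a threshold of 38.5°C or higher.

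The DLT count feeds the rules in Section 5.2.1. With one event among the first three patients, "If 1 of the initial subjects experiences DLT, then 3 additional subjects (to a total of 6 subjects) will be enrolled in the dose level". At six patients, "If it is found that 2 or more of the 6 subjects in a dose level encounter DLT, then the MTD has been exceeded".

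Section 5 reports the outcome for levels 1 to 4: "No DLTs were seen during the Phase I portion". Levels 5 and 6 (Table 3) are tested in "a minimum of 3 patients and a maximum of 6 patients following a standard dose escalation design at additional dose levels". Section 5.3 then sets the consequence: "If a dose level in the parallel Phase I study is found to be tolerable", an expansion cohort of 30 follows.

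**The concern.** A DLT definition has to give the same answer for the same patient at every site. This one pairs two temperatures that are not equivalent. The study is multicentre, and nothing in the protocol names the governing unit. Two sites could each follow the text, one reading in Fahrenheit and one in Celsius, and classify the same fever differently.

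Two things depend on the classification. The first is the cohort decision, because in groups of 3 to 6 a single event can change it. The second is the patient's own treatment. Section 5.2.2 bars Cycle 1 dose modification unless a DLT has occurred, and at level 1 or above it requires treatment to be held when one does.

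**Working it through.** **Inputs.** The cut-offs 101°F and 38.5°C are from Section 5.2.2. The Table 5 cut-off is ≥38.5°C. The cohort rules are from Sections 5.2.1 and 5.2.3. The dosing days are from Section 5.

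**Step 1: try to reproduce the bracketed figure.**

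- °C = (°F − 32) × 5/9, so 101°F = 69 × 5/9 = 38.33°C, which rounds to 38.3°C and not 38.5°C.
- °F = °C × 9/5 + 32, so 38.5°C = 69.3 + 32 = 101.3°F.
- The gap is 38.5 − 38.33 = 0.17°C, or 101.3 − 101 = 0.3°F.

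The stated equivalence is not reproduced in either direction.

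**Step 2: find the readings that are classified differently** (0.1° resolution, with the strict inequality applied to both figures).

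| Reading | Converted | >101°F | >38.5°C | ≥38.5°C (Table 5) |
|---|---|---|---|---|
| 38.3°C | 100.94°F | no | no | no |
| 38.4°C | 101.12°F | **yes** | **no** | no |
| 38.5°C | 101.30°F | **yes** | **no** | yes |
| 38.6°C | 101.48°F | yes | yes | yes |

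On a Fahrenheit scale the discordant readings are 101.1 (38.39°C), 101.2 (38.44°C) and 101.3°F (38.50°C). At 101.0°F neither form is met, and at 101.4°F (38.56°C) both are.

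**Step 3: effect of one reclassified patient on the cohort decision.**

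| DLT count becomes | Consequence |
|---|---|
| 0/3 → 1/3 | three more patients instead of moving on |
| 1/3 → 2/3 | MTD exceeded |
| 1/6 → 2/6 | MTD exceeded |
| 0/6 → 1/6, 2/3 → 3/3, 2/6 → 3/6 | no change |

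**Step 4: would another DLT criterion catch the patient anyway?**

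- Grade 4 neutropenia is a DLT at any temperature, but only if it lasts more than 7 days.
- Non-haematologic toxicity of Grade 3 or above is a DLT if it lasts more than 72 hours or requires a dose reduction. It could catch an accompanying drug-related event.
- The dose-intensity item reads "Patients who are unable to receive 75% of the required doses of both agents secondary to toxicity". Each drug has six Cycle 1 doses: carfilzomib on Days 1, 2, 8, 9, 15 and 16, and panobinostat on Days 1, 3, 5, 15, 17 and 19. Counting per drug, one missed dose leaves 5/6 = 83% and two leave 4/6 = 67%. At least two doses must therefore be lost before this item applies.
- A fever after Day 19 costs no Cycle 1 doses, so the dose-intensity item cannot catch it.

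A short neutropenic fever of 38.4°C late in the cycle can pass all of these.

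**The case against.** The best reply is that the inequality sits on 101°F and the bracket is only a loose conversion, so Fahrenheit plainly governs. The trial also runs under US regulation, and Table 5 serves dose adjustment, not the DLT count. That is a reasonable reading, and it supports keeping 101°F in the correction. It does not remove the problem: the protocol never says so, and the only free-standing Celsius threshold in it is 38.5°C.

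The 38.5°C example does depend on the strict sign carrying into the bracket. That is the natural reading, but if Celsius were taken as 38.5 or higher, as in Table 5, only 38.4°C (101.1 and 101.2°F) would be discordant.

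It is also fair that the practical effect is remote. A decision changes only if a treatment-related Cycle 1 neutropenic fever peaks inside 0.17°C, no other criterion applies, the site uses the Celsius figure, and the cohort stands at a count where one event matters. The vital signs listed in Sections 7.2 and 7.3 do not include temperature, so fever will be found ad hoc, and the wording gap is probably not the main source of measurement uncertainty. These points bear on severity, and they are why the concern is rated minor. They do not make the two figures agree.

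**Conclusion.** The concern holds. Section 5.2.2 states a decision threshold in two units that differ by 0.17°C (0.3°F), and the Fahrenheit and Celsius forms disagree at 38.4°C and, with the strict inequality, at 38.5°C. The exposure is confined to dose levels 5 and 6, where one event can change the path of a cohort of 3 to 6 patients and hence whether a 30-patient expansion opens.

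The documents give no febrile-neutropenia rate and no temperature distribution, so the probability of a fever in the band cannot be estimated. Nothing in them shows that one occurred. The primary response analysis, its alpha and its power do not depend on this point. The arithmetic is certain and the expected effect is small.

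**What to change.** In Section 5.2.2, write the cut-off as >101°F [38.3°C]. This keeps the figure that already carries the inequality and is the more inclusive choice for a safety criterion. It also classifies every 0.1°C reading the same way in both units, because 38.3°C is 100.94°F and 38.4°C is 101.12°F. To avoid a new edge case, say that Fahrenheit governs or that converted readings are rounded to one decimal: 101.0°F is 38.33°C, which rounds to 38.3°C and is not above it.

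The alternative, ≥38.5°C [101.3°F], would match Table 5. However, 38.4°C would then no longer count, so it narrows the DLT definition relative to 101°F and is more than a correction of the conversion.

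Apply the chosen figure to all Cycle 1 neutropenic fevers at levels 5 and 6. The amendment history mentions level 5 from March 2013 and adds level 6 in October 2013, so their DLT periods may already be over, although the documents do not say. If they are, report which figure was used and whether any fever fell in the band.

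The cost is one line of text and a short look at existing records, with no new data or patients. Section 13.1 requires amendments to be approved by the sponsor, both drug suppliers and the principal investigator and submitted to the IRB, so the change is best carried in the next amendment made for other reasons.

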### **1.2.3. Phase Ib Study in Patients with MM**

The primary objective of the CLBH589B2207 trial is to determine the maximum-tolerated dose (MTD) of oral panobinostat when combined with bortezomib in patients with relapsed or refractory MM. A total of 38 patients have been enrolled into five completed dose cohorts: (I) 10 mg panobinostat (TIW) + 1.0 mg/m^2 bortezomib (IV, Days 1, 4, 8, 11) q 21-days, (II) 20 mg panobinostat + 1.0 mg/m^2 bortezomib, (III) 20 mg panobinostat + 1.3 mg/m^2 bortezomib and (IV) 30 mg panobinostat + 1.3 mg/m^2 bortezomib, (V) 25 mg panobinostat +1.3 mg/m^2 bortezomib. Enrollment into Cohort VI at 20 mg panobinostat + 1.3 mg/m^2 bortezomib has enrolled 1 patient as of the 09-Oct-03 cutoff. In Cohorts I-V, the median number of prior therapies was two (range 1-7); 30 patients had at least one prior auto-SCT. Out of 22 bortezomib pre-treated patients 13 were refractory to prior bortezomib therapy (10 PD and 3 SD on bortezomib according to IMWG'08). Median time on study was longest in Cohort 3 at 109 days (range 7- 424) (Anderson et al. 2010).

The combination of panobinostat and bortezomib was safe and tolerated in Cohorts I, II, III and IV. Dose-limiting toxicities (DLT) were reported in cohorts II (one patient with Grade 4 afebrile neutropenia) and cohort IV (4 DLTs: 2 Grade 4 TCPs, requiring 2 consecutive platelet transfusions), Grade 3 pneumonia and Grade 3 fatigue. In cohort V, the dose of panobinostat was de-escalated to 25 mg. In this Cohort, one DLT has been seen to date (Grade 4 thrombocytopenia, Grade 3 asthenia, Grade 3 dizziness).

Hematological AEs have been common, including Grade 3/4 TCP (30 in 38 patients), neutropenia (23) and anemia (6). Non-hematological AEs (all grades) included diarrhea (23), fever (17), nausea (18), fatigue (16), and asthenia (13). A total of 2,200 ECGs have been analyzed: no QTcF prolongations from BL >60 msec nor absolute QTcF time duration >480 msec were noted. No QTcF prolongation ≥Grade 1 were seen.

Although Grade 3/4 TCP occurred frequently it was manageable with dose reduction/interruption and platelet transfusion. TCP (Grade 4) was to be managed by platelet transfusions before study drug dose omission/reduction was allowed. Thrombocytopenia as the DLT in three patients in cohorts IV and V. No patients experienced hemorrhagic events in association with Grade 3/4 TCP. A detailed review

[figure not shown]

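### The platelet DLT bullets in Section 5.2.2 are not ordered by severity: Grade 4 thrombocytopenia of 7 days or less with Grade 2 bleeding can go uncounted, while the same bleed at Grade 3 is a DLT

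*Combined protocol and SAP*

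**What the plan says.** The DLT list in Section 5.2.2 has two platelet bullets. The first is "Grade 3 thrombocytopenia with" bleeding of Grade 2 or higher. The second is "Grade 4 thrombocytopenia (platelets <25,000" per µL) lasting "> 7 days (patients may receive platelet support/transfusion"); it does not mention bleeding.

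Two other bullets might catch a bleeding patient:

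- The non-hematologic bullet, which starts at Grade 3: "Grade 3 non-hematologic drug-related toxicity (excluding alopecia) despite optimal supportive care lasting >72 hours or requiring a dose reduction in the first cycle".
- The dose-intensity bullet: "Patients who are unable to receive 75% of the required doses of both agents secondary to toxicity".

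The same section adds: "Dose modifications are not permitted during Cycle 1 in any cohort unless the subject experiences a DLT". Table 5 in Section 6.1, under its dose modification columns, interrupts both drugs for Grade 3 or Grade 4 thrombocytopenia. It gives Grade 3 as 25 to below 50 x 10^9/L and Grade 4 as below 25 x 10^9/L.

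Sections 5.2.1 and 5.2.3 turn the DLT count into decisions. No DLT in 3, or 1 in 6, allows escalation; 2 or more means the MTD has been exceeded; the MTD is the highest level with at most 1 DLT in 6. Section 5 reports that the four Phase I levels produced no DLTs and takes level 4 into Phase II.

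**The concern.** A DLT list should not score a worse event as safer than a milder one of the same kind. Here the bleeding bullet names Grade 3 alone. The at-least sign is present for the bleeding grade in that same bullet and for the neuropathy and non-hematologic bullets, so its absence before the platelet grade reads as part of the rule. No general clause says that a higher grade satisfies a lower-grade bullet.

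The gap matters because each decision rests on 3 to 6 patients and thrombocytopenia is the main expected toxicity. Section 1.2.3 states: "Hematological AEs have been common, including Grade 3/4 TCP (30 in 38 patients"). The transfusion allowance in the Grade 4 bullet could also widen the gap. A transfusion may shorten the measured time below 25,000/µL, and a bleeding patient is a plausible recipient. The bullet does not say how transfused days are counted.

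**Working it through.** The plan states no figure that depends on this rule, so the check is of its logic, followed by a labelled illustration.

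**Step 1. Apply the two platelet bullets as written.** Bullet (a): platelet grade equals 3 and bleeding grade is at least 2. Bullet (b): platelet grade equals 4 and duration exceeds 7 days.

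| Platelets | Days | Bleeding | (a) | (b) | Platelet DLT |
|---|---|---|---|---|---|
| Grade 3 | 5 | Grade 2 | yes | no | yes |
| Grade 4 | 5 | Grade 2 | no | no | **no** |
| Grade 4 | 7 | Grade 2 | no | no | **no** |
| Grade 4 | 8 | Grade 2 | no | yes | yes |
| Grade 4 | 5 | Grade 3 | no | no | **no** |

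Rows 1 and 2 show the inversion. In rows 2 and 3 the bleed is below the Grade 3 floor of the non-hematologic bullet. In row 5 it reaches that floor, but counts only if it lasts more than 72 hours or requires a dose reduction.

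**Step 2. Test the 75% bullet.** Cycle 1 has six doses of each drug: carfilzomib on Days 1, 2, 8, 9, 15, 16 and panobinostat on Days 1, 3, 5, 15, 17, 19. Since 0.75 x 6 = 4.5, one missed dose (5/6 = 83%) passes and two (4/6 = 67%) fail. The bullet can mean that both drugs fall below 75%, or that either does.

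| Doses held | Carfilzomib | Panobinostat | DLT if both must fail | DLT if either fails |
|---|---|---|---|---|
| Days 8-14 | 4/6 | 6/6 | no | yes |
| Days 9-14 | 5/6 | 6/6 | no | no |
| Days 15-21 | 4/6 | 3/6 | yes | yes |
| Days 16-22 | 5/6 | 4/6 | no | yes |
| From Day 20 | 6/6 | 6/6 | no | no |

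Section 6.4.6 puts carfilzomib platelet nadirs between Day 8 and Day 15, so the expected window includes both caught and missed cases. The table also assumes that doses are held. A patient without a DLT may have no dose modification in Cycle 1 under Section 5.2.2, yet Table 5 interrupts both drugs for Grade 4. The two passages give different instructions for this patient.

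**Step 3. Effect on one cohort.** If one patient has the uncounted event:

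- 1/3 becomes 0/3, so the trial escalates instead of adding three patients.
- 2/6 becomes 1/6, so the level passes instead of exceeding the MTD.

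**Step 4. Illustration; all rates are assumptions.** Let p be the counted DLT rate and u the share of patients whose only limiting event is the uncounted one. The chance of escalating from a level under Section 5.2.1 is E(p) = (1-p)^3 + 3p(1-p)^2 x (1-p)^3. As written the rule gives E(p); if the event counted it would give E(p+u).

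- p = 0.20, u = 0.05: 0.709 against 0.600.
- p = 0.25, u = 0.05: 0.600 against 0.494.
- p = 0.30, u = 0.05: 0.494 against 0.396.
- p = 0.25, u = 0.02: 0.600 against E(0.27) = 0.389 + 0.81 x 0.5329 x 0.389 = 0.557.

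The difference is about 0.10 to 0.11 if 5% of patients have the event, about 0.04 if 2% do, and nil if none do.

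**The case against.** The best case against has four parts.

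- **Rarity.** The study cited for the high thrombocytopenia rate also reports, in Section 1.2.3, no hemorrhagic events associated with Grade 3/4 thrombocytopenia. Taking its 38 patients as the denominator, the exact 97.5% upper limit for any such bleed is 1 - 0.025^(1/38) = 9.3%. The event at issue is narrower: Grade 4, short, in Cycle 1, treatment-related and missed by every other bullet. This stands. The partner there was bortezomib rather than carfilzomib, so it does not settle the rate here, but large assumed rates have no support.
- **Backstop.** The 75% bullet catches some of these patients. This also stands. A reader might infer that the event is never a DLT; Step 2 shows that this is too strong. The bullet does not close the gap, because it depends on onset day, on an ambiguous phrase and on whether doses may be held at all.
- **Sensible reading.** An investigator may treat Grade 3 as a minimum, or count a bleed seen while platelets pass through the Grade 3 range. The text provides for neither, so sites could score the same patient differently.
- **No demonstrated harm.** A reader might infer that the DLT-free result at levels 1 to 4 is wrong, or that patients at levels 5 and 6 have been mis-scored. The documents support neither. They do not say whether such an event occurred, and Section 5 describes the additional levels as still to come. The Phase II sample size does not depend on this point.

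**Conclusion.** The concern holds as a defect in the scoring rule. Read literally, Grade 4 thrombocytopenia of 7 days or less with Grade 2 bleeding meets neither platelet bullet nor the non-hematologic bullet, and becomes a DLT only if the 75% bullet happens to apply. The milder Grade 3 event with the same bleed is always a DLT when treatment-related and in Cycle 1.

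One such patient is enough to change an escalation or MTD decision. How often that would happen cannot be derived from the documents and may be low, so the probabilities in Step 4 show sensitivity only and do not estimate an effect in this trial. The conclusion assumes that the bullet's wording is as intended, with no at-least sign omitted before the platelet grade.

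**What to change.** Three changes, all for the sponsor to word, because a Cycle 1 DLT also triggers a treatment hold, discontinuation at level -1 and permission to modify doses:

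1. Reconcile the two platelet bullets in Section 5.2.2 so that a more severe platelet grade with the same bleed is not scored as less limiting. State how Grade 4 of 7 days or less with bleeding is scored, and whether the 75% bullet needs one drug or both to fall short.
2. Reconcile the Cycle 1 ban on dose modification without a DLT (Section 5.2.2) with the interruptions in Table 5 (Section 6.1).
3. Re-check the Cycle 1 platelet, bleeding and dosing data of patients already treated against the reconciled definition. Do this before relying on the statement in Section 5 that no DLTs were seen, and before declaring any additional level tolerable.

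The cost is a few words of protocol text and a re-read of small cohorts. The downside is that the DLT count may become less favourable.
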